Adolescent Responses to Varying Environments in Virtual Reality Simulations

NCT04465240

April 4, 2024

Study Protocol

This study is a randomized experiment of the influence of different virtual neighborhoods on emotion and stress reactivity in adolescents and to determine if neighborhood exposures and chronic stress moderate the response to virtual neighborhood conditions. It was approved by the University of Southern California Institutional Review Board.

Enrollment inclusion/exclusion criteria. In order to be eligible for the study youth must be (a) age 14-17, (b) English-speaking, (c) able to use and manipulate a joystick/controller and provide physical and physiological measurements, (d) not pregnant, by self-report, (e) in good physical and mental health, with no self-reported history of hypertension, cardiovascular disease (CVD) or CVD treatment (with associated medication list indicative of treatments that result in exclusion), and (f) have hair at least 1cm in length based on self-report to be able to provide a hair sample.

Informed consent. After recruitment, the consent and assent process was completed, with forms completed securely electronically. We first explained the study to the parents/guardians and adolescent, and if they agreed to participate, parents/guardians provided electronic written consent online. The adolescent completed a brief eligibility screen, and if eligible subsequently provided electronic written assent online.

Pre-session questionnaires. Prior to the study session, youth participants and their primary caregiver were each invited to complete a set of questionnaires using a secure online system, REDCap. If not completed prior to the session, youth first completed these questionnaires during the study session.

Study Session Procedures. Each participant completed one single study session, with no follow-up. At the study session, participants completed additional questionnaires, cognitive tasks, provided a hair sample for analysis of cortisol concentration, and completed measures of height and weight. Participants were then oriented to the virtual reality (VR) task and learned how to navigate in VR. Subsequently participants watched a nature video for approximately 20 minutes to establish a baseline for reactivity assessment. Next, participants navigated the VR neighborhood condition they were randomly assigned to, using a head mounted device. After the VR task, participants completed post-task measures and additional questionnaires, and then a 30-minute recovery period watching a nature video.

Virtual Neighborhood Environment and Task. Two virtual neighborhoods were designed to represent disadvantage and affluence, based on empirical literature highlighting characteristics such as building and business types, signals of social processes, the level of upkeep or deterioration, presence of amenities, green space, and more. They contain background city noise and are populated by human avatars that are walking, standing and conversing. The avatars are held constant across the two neighborhoods, reflect the overall demographics of the U.S., and are balanced to ensure that avatar type (e.g. professional, casual, etc.) is not biased by race/ethnicity or gender. As part of the session participants first learn to navigate the VR environment in a desktop environment. Participants then entered a VR neighborhood, to which they were randomly assigned, that was presented using a head mounted device. Participants are asked to navigate and explore a set route and collect a series of gems that are placed throughout the route. Routes were expected to take approximately 10-15 minutes to navigate on average, though participants time varied as they are allowed to go at their own speed.

Measures: Primary Outcomes

- Emotion: After the VR session, participants rated the emotions they felt while they were in the VR neighborhoods. They rated how strongly they felt positive emotions, such as amusement

and contentment; negative emotions such as fear, disgust, sadness, and anger; complex emotions such as compassion; as well as affect and arousal/alertness.

- HPA-axis function: Cortisol. Participants gave saliva samples by passive drool for assay of salivary cortisol. Samples were provided after baseline, after completion of the VR neighborhood task, after questionnaire completion, after the first 15 minutes of the video during the recovery period, and after the final 15 minutes of the video during the recovery period.

- Psychophysiological reactivity. Electrocardiograph and impedance cardiography signals were recorded continuously, using a standard electrode configuration, allowing for measures such as heart rate variability, pre-ejection period, and cardiac output. Blood pressure was also recorded regularly using standard equipment to support integration with other measures. Recording began just prior to VR orientation to allow time to get used to it. Measures were summarized during baseline, completion of the VR neighborhood task, questionnaire completion, the first 15 minutes of the video during the recovery period, and the final 15 minutes of the video during the recovery period.

Additional post-task measures: Participants completed a brief survey regarding their perceptions and observations of the VR neighborhood, and any feelings of discomfort during VR. In addition, participants rated a set of avatars from the virtual environments on their perception of the avatar's character traits.

Survey measures. Youth and parents completed a demographic questionnaire, and parents completed a residential history for the youth that are geocoded and linked to US census tracts and other sources of neighborhood information. Youth also completed a questionnaire concerning various factors that can influence the quality of saliva and hair samples for cortisol assays. Parents and youth both complete surveys concerning their neighborhood characteristics and pandemic-related stressors. Youth completed surveys to assess current and lifetime exposure to acute and chronic stress, perceived stress and discrimination. Other youth surveys concerned perceptions of parenting, school characteristics, experiences with video games, coping strategies, emotion regulation, health and well-being, and parents and youth report on youth socioemotional functioning.

Additional measures: Executive functions and fluid cognition were assessed using a set of tasks from the NIH Toolbox. Cortisol concentrations in hair will be utilized as a measure of chronic physiological stress, and thus a small hair sample was provided.

Adolescent Responses to Varying Environments in Virtual Reality Simulations

NCT04465240

April 4, 2024

Statistical Analysis Plan

STATISTICAL ANALYSIS PLAN

Prior to analyses we will (a) conduct pre-processing for psychophysiological data, and (b) screen data for quality and integrity, including evidence of significant outliers, variable distributions, and checks for violations of analysis assumptions. Variables will be transformed as needed. We will also conduct a factor analysis to determine if discrete emotion measures can be reduced. We will then test the effectiveness of randomization to virtual neighborhood condition, using *t* tests and chi-square tests, examining group/condition differences in demographics and all potential covariates. Subsequent statistical models will adjust for variables found to differ between experimental groups ($p < .05$).

Analysis will focus on the main effects of the virtual neighborhood condition – neighborhood disadvantage and neighborhood advantage/affluence – on emotional, psychophysiological and neuroendocrine outcomes within the single study session. For measures available at one time point during the study session, after the experiment (e.g. all emotional measures), multiple linear regression models will be used to estimate the mean difference in outcome between groups after controlling for covariates as needed. For outcomes measured repeatedly over the course of the single study session (e.g. cortisol, psychophysiological measures), linear mixed-effect modeling with random effects will be used to account for the lack of independence among repeated measures (level-1) nested within individuals (level-2). With repeated measures we are able to test whether the outcome of interests differs between groups over the course of the single study session, and whether the rate of change or the level at specific important study epochs (e.g. during/after the virtual neighborhood condition) differs between groups. Cortisol is measured at five specific time points during the study session (at the end of baseline, after the virtual neighborhood condition, after completing questionnaires, and after 15 and 30 minutes watching a video). Psychophysiological measures are collected continuously and summarized for specific study epochs during the single study session (baseline, virtual neighborhood condition, questionnaire completion, and the first and final 15 minutes watching a video). For each outcome we will determine the best fitting model to capture change over time, such as linear or polynomial models, piecewise models, or models with time-varying predictors to indicate discrete study session epochs. We will then examine whether study group, or interactions between study groups and time, are significant and thus indicative of group differences in outcomes.

In addition, we will test the moderation effect of variables such as the characteristics of neighborhoods of residence and chronic stress by including an interaction term with study group to see if the effect of VR neighborhood condition differs across the levels of chronic neighborhood exposure or chronic stress. Although the role of sex as a biological variable is not a specific aim of the study, we recognize that sex differences may exist. Therefore, we will examine sex both as covariates and also in their interaction with experimental neighborhood condition, to examine if the effect of virtual neighborhood environment differs by sex.

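### The SAP's only explicit rule for choosing covariates is a p<.05 imbalance test; if that rule is operative, precision is forgone, mainly for the emotion ratings

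*SAP*

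**What the plan says.** The first paragraph of the SAP sets out a check on the allocation: "We will then test the effectiveness of randomization to virtual neighborhood condition". It uses t tests and chi-square tests, "examining group/condition differences in demographics and all potential covariates". The result then determines the models: "Subsequent statistical models will adjust for variables found to differ between experimental groups", at p<.05. The candidate variables are neither listed nor counted.

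The second paragraph says that single-time-point outcomes, which include all emotion measures, go into a linear regression estimating the group difference "after controlling for covariates as needed". No criterion of need is given. Repeated outcomes (cortisol, psychophysiology) go into mixed models. These may test "whether the rate of change or the level at specific important study epochs", and the SAP also looks at whether "interactions between study groups and time, are significant and thus indicative of group differences in outcomes".

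The third paragraph treats sex on its own footing: "we will examine sex both as covariates and also in their interaction with experimental neighborhood condition". Residential neighborhood and chronic stress appear there only as moderators, through interaction terms.

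In the Protocol (Measures: Primary Outcomes), emotions are rated once, after VR. Cortisol and the physiological signals each have a baseline value.

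**The concern.** When assignment is random, a difference between groups in a variable measured before exposure arises by chance. Testing it says nothing about whether the variable is worth adjusting for. What makes a covariate useful is its relation to the outcome, and no sentence in the SAP selects on that ground. Sex is the one variable that comes in for another reason.

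What is at stake is efficiency. The emotion ratings have no baseline value, so covariates are the main way to reduce their residual variance. A comparison of cortisol or physiology at a single epoch can gain in the same way. A rule that looks only at imbalance would usually leave a strong predictor out and would sometimes bring in an irrelevant variable.

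**Working it through.** The documents give no sample size, power, effect size or covariate-outcome correlation, so there is no plan figure to reproduce.

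**From the documents.** Imbalance threshold p<.05 (SAP, first paragraph; sidedness not stated, two-sided assumed). Random assignment to two conditions (Protocol; ratio not stated, 1:1 assumed). One post-VR emotion rating. Sex examined as a covariate.

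**Assumed.** N = 100 or 200. Sex, with R² .03, in every model. One further pre-VR covariate x with incremental R² .05, .10 or .20. Effect d = .557 (N = 100) or .392 (N = 200), chosen to give 80% power with sex alone. Two-sided .05 tests.

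**Step 1: how often the rule selects.** Each pre-VR variable is selected with probability .05. The chance of at least one selection among k independent candidates is 1 − .95^k, which is .23, .40 and .64 for k = 5, 10 and 20.

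**Step 2: fixed adjustment, normal approximation.** Power ≈ Φ(2.80 × √[.97/(.97 − R²)] − 1.96), where 2.80 = 1.96 + .84. For R² .05, .10 and .20 the first term is 2.88, 2.96 and 3.14, so power is about .82, .84 and .88.

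**Step 3: rule against fixed adjustment, simulated.** There were 40,000 trials per cell. The rule adds x only if its t test between groups gives p<.05; fixed adjustment always adds it.

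| N | R² | Power, rule | Power, fixed | Gain (points) | Null rejection, rule | Variance ratio, rule/fixed |
|---|---|---|---|---|---|---|
| 100 | .05 | .798 | .813 | 1.5 | .049 | 1.03 |
| 100 | .10 | .796 | .830 | 3.4 | .046 | 1.08 |
| 100 | .20 | .806 | .878 | 7.2 | .044 | 1.18 |
| 200 | .05 | .799 | .816 | 1.7 | .048 | 1.04 |
| 200 | .10 | .804 | .838 | 3.4 | .048 | 1.08 |
| 200 | .20 | .807 | .880 | 7.3 | .044 | 1.18 |

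x was selected in 4.8–5.3% of trials. Mean estimates under the two strategies agreed within .001 in every cell.

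The variance ratios can be checked by hand. Trials with |z| > 1.96 carry a share 2 × (1.96 × .0584 + .025) = .28 of the variance due to chance imbalance in x, so the rule leaves .72 of it. The ratio is then about 1 + .72 R²/(.97 − R²) = 1.04, 1.08 and 1.19, which agrees with the table apart from the small cost of estimating the slope.

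A second simulation without the sex term (20,000 trials per cell) shows the same pattern. At N = 130, rule against fixed is 79.6/83.1% at R² .10, 79.9/86.9% at .20 and 80.3/90.9% at .30. Null rejection under the rule was 4.1–4.8% over N = 60, 130 and 200.

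**Step 4: repeated outcomes.** If x adds the same amount to every epoch, it cancels from VR minus baseline but not from the level at VR. Random-intercept simulations (intraclass correlation .5 and .7, each contrast sized for 80% power) give:
- Level at the VR epoch: rule .796–.808 over all cells; fixed .812–.819, .835–.842 and .872–.879 for R² .05, .10 and .20.
- VR minus baseline: rule .791–.802, fixed .788–.802. There is no gain.

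**Step 5: many variables screened.** Assume 20 candidates, of which 3 jointly carry the R² (20,000 trials). The expected number selected is 20 × .05 = 1.0. At least one is selected in 64% of trials, and any of the 3 prognostic ones in 1 − .95³ = 14%.
- N = 100: rule .773/.779/.777; the 3 named in advance .799/.824/.866.
- N = 200: rule .782/.797/.796; the 3 named in advance .808/.839/.875.

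Part of this gap is a cost of the rule itself. Adjusting for a variable with imbalance statistic t multiplies the variance of the group estimate by 1 + t²/(N − 2). At t = 1.96 that is 1 + 3.84/98 = 1.04 for N = 100 and 1 + 3.84/198 = 1.02 for N = 200, with nothing recovered if the variable is not prognostic. At N = 100 and R² .05, the named set reaches only the 80% benchmark (.799). The whole 2.6-point gap there comes from the rule falling to .773.

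**The case against.** The strongest reply is that the imbalance rule is not worded as exclusive. The SAP says it will adjust for variables that differ; it does not say that it will adjust for nothing else. The regression sentence leaves room for further covariates. A reader might infer that precision is certainly lost, and the documents do not support that. The power figures for the rule describe the case where this room is never used. What stands is that no criterion governs its use, so any prognostic covariate would be chosen after the data are seen.

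Second, the study is largely about reactivity, and change and group-by-time contrasts gain nothing from covariates with a constant effect across epochs. This is right. It confines the point to the emotion ratings and the level-at-epoch comparisons.

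Third, sex is already covered, and the moderation models would normally carry main effects of neighborhood and chronic stress. This is also fair, but those are additional models and do not adjust the main-effect estimates.

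Fourth, a reader might infer from Step 5 that the rule mostly adjusts for irrelevant variables. That follows only from the assumed 3-in-20 split. The documents give neither the number screened nor the share that is prognostic.

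**Conclusion.** The point holds as a minor matter of efficiency. The only explicit adjustment criterion is unrelated to prognosis, and the wording that could admit better covariates has no content. If the imbalance test is what operates, the loss for a single-time-point outcome is about 2, 3 and 7 power points at assumed R² of .05, .10 and .20 for one covariate. When many variables are screened, chance selections can cost a few points more. All of this rests on assumed N, R² and numbers of candidates. The loss becomes material only near R² .20, and nothing in the documents shows that a covariate reaches that.

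Two stronger readings should be resisted. One is that the rule biases the results or inflates false positives. For pre-VR covariates it does neither: mean estimates agree, and type I error is at or slightly below nominal. The other is that the estimates are therefore safe whatever is adjusted for. That assurance does not extend to a covariate measured after VR, because such a variable could differ between groups as a result of the condition. The SAP sets no time limit on its candidates, and the Protocol places some questionnaires after the VR task. Equally, the documents do not say that any post-VR variable will be used, and framing the tests as a check on randomisation suggests otherwise. This calls for a clarifying line and does not establish bias.

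**What to change.** - Delete the p<.05 adjustment rule and report balance descriptively.
- Before outcomes are examined by condition, name a short covariate set for each outcome, chosen for expected association with it, and use that set whatever the observed imbalance. Sex belongs in each set. Outcome-specific candidates among the Protocol's survey measures are youth socioemotional functioning for the emotion ratings and the saliva-quality items for cortisol levels. Neither is shown to predict its outcome.
- Use these only where collection before VR is confirmed. The Protocol's description of survey measures gives no timing, and questionnaires were completed before the session, early in the session and after VR.
- State that only variables measured before VR, or that VR cannot affect, may be covariates. This also gives the undefined covariate wording in the regression sentence a meaning.

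The cost is SAP wording, a check of questionnaire timing and a few degrees of freedom. No new data are needed. If the covariates predict weakly, the gain will be small.

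### For cortisol and psychophysiology, a study-group term that averages in the pre-VR baseline can count as evidence, and no model uses the equality of baseline means that randomisation provides

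*SAP*

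**What the plan says.** The Protocol (Study Session Procedures) places the baseline before exposure: "Subsequently participants watched a nature video for approximately 20 minutes to establish a baseline for reactivity assessment". The assigned neighborhood comes next. For cortisol, the Protocol (Measures: Primary Outcomes) lists five saliva samples, beginning: "Samples were provided after baseline, after completion of the VR neighborhood task, after questionnaire completion". The SAP paragraph on main effects treats psychophysiology the same way, with data "summarized for specific study epochs during the single study session (baseline, virtual neighborhood condition, questionnaire completion" and two recovery segments. All five occasions are responses in the mixed model.

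That paragraph names several targets. One is "whether the outcome of interests differs between groups over the course of the single study session"; others are "whether the rate of change or the level at specific important study epochs (e.g. during/after the virtual neighborhood condition) differs between groups". The form of time is to be the best-fitting one for each outcome, "such as linear or polynomial models, piecewise models, or models with time-varying predictors to indicate discrete study session epochs". The decision sentence follows: "We will then examine whether study group, or interactions between study groups and time, are significant and thus indicative of group differences in outcomes". A significant group term or a significant group-by-time interaction then counts as a group difference.

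The only adjustment rule is in the SAP's opening paragraph: "Subsequent statistical models will adjust for variables found to differ between experimental groups", judged at p < .05. Neither document says that the baseline value of the outcome is an adjuster or that the arms share a baseline mean. Emotion is rated once, after VR, so it is not affected.

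**The concern.** Cortisol and psychophysiological reactivity are two of the three primary outcome domains. The baseline cannot carry a condition effect, yet it is one of the five responses behind a term whose significance alone is enough for a conclusion. Depending on the coding eventually chosen, that term is either a diluted average or a comparison of the arms before they were treated differently.

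The second issue is precision. Randomisation makes the baseline means equal in expectation. A model that ignores this gives up information already collected. The balance rule does not recover it: even if baseline outcome values count as covariates, the rule adjusts for them only when the arms differ at p < .05, which under randomisation happens about 5% of the time per measure.

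**Working it through.** **Inputs.** From the documents: five occasions, one before VR and four after, and the either/or decision rule. The documents give no sample size, SD, within-person correlation or expected time course, and p < .05 is stated only for the balance check. Assumed for illustration: SD 1 at each occasion, known covariance, two-sided 5% tests, and correlation ρ from 0.5 to 0.8 with compound symmetry unless stated. There is no figure in the plan to reproduce.

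**1. What the group term estimates (design only).** With no interaction and equal weights, and a condition effect d:
- sustained over all four later occasions: (0 + d + d + d + d)/5 = 0.8d;
- VR epoch only: (0 + d + 0 + 0 + 0)/5 = 0.2d.

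With an interaction and baseline as the reference level, the term is the baseline difference, with expectation 0 whatever happens later.

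**2. Precision at one post-baseline epoch (separate epoch means).** The variance is 1 for the raw level, 2(1 − ρ) for change, and 1 − ρ² with a common baseline mean. These formulas need only equal variances and the baseline-to-epoch correlation.

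| ρ | common baseline | change | cut vs change, (1 − ρ)/2 | cut vs raw level, ρ² |
|---|---|---|---|---|
| 0.5 | 0.75 | 1.00 | 25% | 25% |
| 0.6 | 0.64 | 0.80 | 20% | 36% |
| 0.7 | 0.51 | 0.60 | 15% | 49% |
| 0.8 | 0.36 | 0.40 | 10% | 64% |

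**3. Power of the group term alone.** Scale a sustained effect so that the baseline-adjusted mean of the four later epochs has 80% power (standardised effect 1.96 + 0.84 = 2.80). The variance of that mean is (1 + 3ρ)/4 − ρ², and that of the group term is (1 + 4ρ)/5.
- ρ = 0.5: variances 0.375 and 0.60; 0.8 × 2.80 × √(0.375/0.60) = 1.77, power 43%.
- ρ = 0.8: variances 0.21 and 0.84; 0.8 × 2.80 × √(0.21/0.84) = 1.12, power 20%.

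Under AR(1) over the same range of ρ, the group term has 63% falling to 40%. For a VR-only effect, scaled so that the adjusted VR-epoch contrast has 80%, it has 10% falling to 7% under compound symmetry.

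**4. The SAP's rule as written.** Under compound symmetry the averaged group term and the 4-df interaction test are independent, so power is 1 − (1 − p₁)(1 − p₂).
- Sustained: ρ = 0.5, 1 − (1 − 0.425)(1 − 0.374) = 64%; ρ = 0.8, 1 − (1 − 0.202)(1 − 0.512) = 61%.
- VR-only: ρ = 0.5, 1 − (1 − 0.096)(1 − 0.686) = 72%; ρ = 0.8, 1 − (1 − 0.066)(1 − 0.775) = 79%.
- No effect: 1 − 0.95² = 9.75%. Across the codings examined the rate was about 9-10%.

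**5. A joint test that needs no choice of epoch.** In the common-baseline model, test the four post-baseline group terms together (4 df, 5% level). Same scalings as above:

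| Effect | 4-df joint test, common baseline | SAP's 4-df group-by-time test | SAP's either/or rule (about 10% false positives) |
|---|---|---|---|
| Sustained | about 60% | 37-51% | 61-64% |
| VR epoch only | 71-78% | 69-78% | 72-79% |

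**The case against.** The strongest reply is that the SAP does not depend on the group term. It also accepts interactions, and it names rate of change and epoch levels, all of which are valid. This stands. A reader might infer from step 3 that the plan has little chance of detecting a brief effect. The documents do not support that: the 7-10% describes one term, while the either/or rule has 72-79%. Nor does the SAP say that it would report a baseline-coded group coefficient as a condition effect; its decision sentence merely fails to exclude it. Having baseline among the responses does not inflate error either. Each single test holds its level, and the 9-10% comes from accepting either of two terms.

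It can also be said that the precision gain is conditional. This stands in part. A level read from a fitted linear trend, which the SAP allows, has variance ρ + 0.3(1 − ρ) with five equally spaced occasions, at the first one after baseline. That is 0.65 at ρ = 0.5, below the 0.75 for the adjusted single epoch, provided the linear shape is right. At ρ = 0.8 it is 0.86 against 0.36. Within the linear coding itself, a common baseline still cuts the variance of the change contrast by 9-25%.

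Finally, the power ranges rest on an assumed correlation structure, as the AR(1) results show. Only the 0.8 and 0.2 dilution follows from the design alone.

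**Conclusion.** The point holds as a free improvement in how baseline is handled and in what the group term may be used for. Dilution to 0.8 or 0.2 requires no interaction and equal epoch weights. The variance cuts of 10-25% against change and 25-64% against the raw level require separate epoch means, equal variances and the assumed ρ of 0.5-0.8. The group-term power figures (20-43% for a sustained effect under compound symmetry, 40-63% under AR(1)) are illustrative and concern that term only.

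A reader might go further and conclude that the SAP should rest each outcome on one named epoch contrast at no cost. The documents do not support this, because they state no expected time course. With an assumed 63 per arm, a peak effect of 0.5 SD, ρ = 0.5 and effects of 0.5, 1, 0.75 and 0.5 of the peak over the four later epochs, the adjusted VR-epoch contrast has power 0.37 against 0.51 for the existing group term. Conversely, the adjusted four-epoch mean has only 15-17% for a VR-only effect, where the SAP's 4-df test has 69-78%.

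**What to change.** For each repeated outcome, state in the SAP that:
- the mixed model has a common baseline mean, that is, epoch terms plus group-by-post-baseline-epoch terms and no group term at baseline;
- the condition effect is taken from the post-baseline terms, for which the 4-df joint test requires no choice of epoch;
- a stand-alone group term that includes baseline is not counted as evidence;
- if a trend or piecewise coding is used instead, the arms share the same baseline value in that coding;
- baseline outcome values are not left to the p < .05 balance rule.

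The cost is SAP wording and one model line, with no new data. Estimating the baseline relation uses about one degree of freedom, roughly 1/(N − 4) of variance: 1/56 = 1.8% at an assumed total N of 60 and 1/196 = 0.5% at 200. Keeping baseline as a response with a common mean retains participants who lack a baseline value; using it as a covariate would lose them.

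Naming one primary post-baseline contrast per outcome is optional. It would remove the either/or false-positive rate of about 9-10% (if each term is tested at 5%), but it loses power if the effect falls in other epochs. If the sponsor chooses it, the SAP should give the expected time course that justifies the contrast and keep the joint test as secondary.
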